### 3.2. Design and Methods

**3.2a. Overview.** Following a 1-week run-in phase, ten young adults aged 18 to 30 years with T1DM ( $\geq 1$  year) and who experience FOH will be randomized to an intervention or attention control group. The intervention group will participate in eight weekly one-hour sessions using a CBT-based approach (FREE), wear a RT-CGM device, and keep a daily diary. The attention control group will also wear a RT-CGM device for 8 weeks but will not participate in weekly sessions and will not keep a diary. Data will be collected: (1) at the beginning of a 1-week run-in period (week 0); (2) at completion of the intervention at the end of 8 weeks (week 8); and (3) post-program at 12 weeks. At completion, FOH, self-management, and A1C will be measured and RT-CGM recordings will be analyzed to determine within-group and between-group differences.

**3.2b. Setting and Sample.** The study intervention will take place at the University of Illinois at Chicago (UIC) Medical Center and College of Nursing. Inclusion criteria: (1) 18-30 years old, (2) diagnosed with T1DM  $\geq 1$  year and receive medical care from an endocrinologist, (3) use insulin pump therapy, and (4) have self-reported FOH (screening questionnaire). Exclusionary criteria: (1) pregnant or breastfeeding, (2) actively treated for a mental health condition, (3) have a co-existing chronic illness or taking medications (excluding insulin) that may influence diabetes self-management or GV.

**3.2c. Recruitment.** Subjects will be recruited through Chicago metropolitan area university medical centers, local diabetes websites, and organizations using flyers, e-announcements, and recruitment letters. At UIC, we will identify potentially eligible subjects through the electronic medical record system and send recruitment letters. The University of Illinois clinics saw over 900 patients with T1DM; thus, there is a sufficient pool from which to recruit. We have been successful in recruiting using these methods for our previous studies.

**3.2d. Sample Size Determination.** The sample size of 10 subjects ( $n = 5$  intervention group; 5 intention control group) will be sufficient to test the feasibility of the study protocol and to obtain preliminary outcome measures.

**3.2e. Procedures.** Study staff will screen subjects for inclusion/exclusion criteria. Scores of 3 or 4, indicating that worry occurs *often* or *very often*, on any item on the worry scale (4-point Likert) of the Hypoglycemia Fear Scale (HFS-2) will be used to determine the presence of FOH (personal communication [name], 5/26/15). Those who meet the study criteria will be scheduled for an appointment at the College of Nursing for the start of the 1-week run-in period to: obtain consent and baseline measures (Table 1, Week 0) and apply a RT-CGM device with instructions provided on its care. Following the 1-week run-in period, subjects will be randomized to the FREE intervention or attention control group. During the study period, subjects will continue to receive their usual diabetes care with their health care provider. The subjects will be encouraged to discuss any questions regarding blood glucose management with their diabetes health care provider.

**3.2e1. FREE Intervention.** Subjects randomized to the FREE intervention group will: (1) attend eight weekly one-hour sessions based on principles of CBT and exposure treatment for specific phobias. The program will consist of 8 weeks of individual sessions (weeks 1-8), in which participants will be taught cognitive restructuring and exposure-based techniques to decrease their FOH. Treatment will target incorrect beliefs about hypoglycemia, hypervigilance to symptoms, fear of symptoms, and maladaptive behavioral responses in response to glucose levels. Participants will create a fear and avoidance hierarchy and be taught to begin approaching previously feared situations (e.g., spending time alone, reducing snacking, allowing glucose readings to reach lower safe levels, etc.) to experience habituation and the resulting decrease in anxiety. To maintain treatment fidelity, sessions will follow a manualized protocol (See Appendix A. Outline of FREE Intervention). Additionally, sessions will be audiotaped and reviewed for fidelity to the treatment protocol. Weekly homework will be assigned to reinforce the program content. (2) FREE intervention subjects will continue to wear a RT-CGM for the 8-week period and complete a daily FOH diary. RT-CGM recordings and daily diaries will serve as cues for glucose and fear levels. At each weekly visit, participants will receive a copy of their RT-CGM recordings for the previous week and (3) have their RT-CGM site changed by a study staff member who is a registered nurse.

**3.2e2. Attention Control Group.** Subjects randomized to the attention control group will have (1) an initial meeting with study staff (study week 1) to review study purpose and goals, (2) continue to wear a RT-CGM for the 8-week session; and (3) return to have their RT-CGM site changed weekly by study staff (registered nurse). The weekly visits for RT-CGM site changes will facilitate keeping the attention control group engaged

and will assure proper replacement of the glucose sensor (Appendix D).

**3.2e3. Subject Retention Strategy.** Both the FREE intervention group and the attention control group will (1) wear a RT-CGM; (3) receive reminders of their next appointment; and (4) have weekly visits to change the RT-CGM site. The weekly appointment reminders and RT-CGM site changes will be used to facilitate subject retention. Those in the FREE group will (5) receive additional intervention sessions week 1-8 and (6) weekly CGM downloads with GV analysis when they attend each session. (7) All subjects will be compensated for their time.

### 3.2f. Measures.

**3.2f1. Baseline and Post-Intervention Measures.** *Self-report instruments* will be used to obtain demographic and health information, previous history of hypoglycemia, fear of hypoglycemia, self-management behaviors, and related variables (self-efficacy, anxiety, diabetes distress). The scales have strong psychometric properties and have been validated in T1DM populations (Table 1). *Glycemic control* will be measured with a fingerstick for A1C for assessment of longer-term glycemic control using A1C Now® (Chek Diagnostics, Indianapolis, IA).

**3.2f2. Ongoing Measures: Diary.** A daily diary will be used to measure daily fear levels and perceptions of GV for FREE participants only.

Table 1. Measures		
Variables	Measure	Frequency
Aim 1 Feasibility		
Recruitment Retention Acceptability	Number of eligible respondents/Number consented Attendance rate; Completion rate Participant evaluation (Appendix C)	Ongoing Weekly Week 8
Aim 2 Program outcomes		
Previous hypoglycemia	Hypoglycemia Patient Questionnaire 	Week 0
FOH	Hypoglycemia Fear Scale (HFS-2  ) FREE group only: Daily FOH Diary: Fear level  (Appendix B)	Week 0, Week 8, 12 Daily
Glycemic measures Glycemic control Glycemic variability	A1C (A1C Now®) RT-CGM (Dexcom®): Daily glucose standard deviation (GlucSD), continuous net glycemic action (CONGA), coefficient of variation (CV%), interquartile range (IQR) and mean amplitude of glycemic excursions (MAGE) (see 3.2f3) FREE group only: Daily FOH diary: GV perception  (Appendix B)	Week 0, Week 8, 12 Daily
Perception of glycemic variability		Daily
Diabetes self-management	Diabetes Self-Management Questionnaire 	Week 0, Week 8, 12
Other psychological covariates to characterize sample: self-efficacy, anxiety; mood, diabetes distress	Self-Efficacy for Diabetes  PROMIS Anxiety and Depressive Mood Scales Diabetes Distress 	Week 0, Week 8, 12 Week 0, Week 8, 12 Week 0, Week 8, 12

**3.2f3.Ongoing Measures: Glycemic Variability.** Subcutaneous interstitial glucose levels will be monitored during the run-in phase (over a period of 7 days) and the 8-week intervention (FREE intervention and attention control groups) using a Dexcom G4 Platinum® (San Diego, CA). A glucose sensor and recorder will be placed on the abdomen and changed weekly by a trained study staff member (a registered nurse). All subjects will be able to view their RT-CGM values. At the end of each week, all data will be downloaded to the Dexcom Software and examined for glycemic trends and excursions. The weekly glucose summary will be provided to subjects in the intervention group at each weekly session to provide feedback on their glucose trends. Those in the attention control group **will be able to view** their CGM readings in real-time but **will not** receive weekly summaries. Rather, at the end of the full study (i.e., 12 weeks), they will receive their weekly

summaries.

To analyze GV for study outcomes, the raw data will be downloaded to an EXCEL spreadsheet. The research staff will be trained on data cleaning, confirmation of regular calibration, identification of errors, and review of missing data or time-points. The amount of time spent in hypo- and hyperglycemia will be calculated (% and minutes; < 70 and > 180 mg/dl). GV will be determined by calculating the daily glucose standard deviation (GlucSD), continuous net glycemic action (CONGA), coefficient of variation (CV%), interquartile range (IQR), and mean amplitude of glycemic excursions (MAGE). These are measures that are recommended to obtain a comprehensive evaluation of GV.

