## PROTOCOL

### A Cognitive Behavioral Therapy Intervention (FREE) to Reduce Fear of Hypoglycemia in Young Adults with Type 1 Diabetes

#### 1. ABSTRACT

In persons with type 1 diabetes (T1DM), iatrogenic hypoglycemia is the major limiting factor in achieving optimal blood glucose control. All persons with T1DM are at risk for hypoglycemia (blood glucose level < 70 mg/dl), which is life-threatening and has serious physical symptoms and psychological sequelae that lead to profound fear of future hypoglycemic events. This fear results in greater glucose variability (the intra-day fluctuations in blood glucose), due to under- or overcompensation of food intake, insulin dosing, or physical activity, as well as anxiety, depression, and reduced quality of life. Greater glycemic variability (GV) is associated with a higher risk of hypoglycemia and diabetes complications. Young adults are particularly at risk because they report greater FOH and have poorer glycemic control. A major gap exists in how to manage FOH as a crucial component of diabetes self-care. Our overall objective is to reduce FOH and improve diabetes self-management, glycemic control, and variability in young adults with T1DM. We specifically aim to: (1) Determine the feasibility of an 8-week CBT-based intervention to reduce FOH and (2) obtain means and standard deviations of group differences from baseline to program completion on the outcomes of FOH, self-management, glycemic control and glycemic variability in young adults with T1DM who experience FOH. To achieve these aims, we propose a randomized control pilot trial in 10 young adults aged 18 to 30 years with T1DM. Participants will be screened for FOH levels. Eligible subjects will be randomized to the intervention (Fear Reduction Efficacy Evaluation [FREE]) program or attention control group. A 1-week run-in phase is planned, with baseline measures of FOH and 24-hour real-time continuous glucose monitoring recordings (RT-CGM) to calculate GV for both groups. The intervention group will participate in eight weekly one-hour sessions using a cognitive behavioral therapy (CBT) and exposure treatment for specific fears. RT-CGM and a daily FOH diary will be used as feedback cues. The control group will wear a 24-hour RT-CGM device during the same 8-week period and return for weekly RT-CGM site changes by study staff. At completion, FOH will be measured, and RT-CGM recordings will be analyzed to determine within-group and between-group differences. The findings from this proposed study will serve as the foundation for a larger clinical trial to reduce FOH and improve self-management, glycemic control, and variability. Meeting these goals will have important clinical implications to reduce diabetes complications and improve quality of life in young adults with T1DM.

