### 3.2g. Data Analysis

1. The feasibility of the program will be evaluated by assessment of recruitment, retention, and participant evaluation. Itemized logs of recruitment sites, methods, responses, eligible subjects, and consented subjects will be documented. Retention will be evaluated through documentation of weekly attendance and compliance with RT-CGM site changes. As part of the feasibility assessment, we will also track the number of RT-CGM sensor failures, RT-CGM placement sites, time to failure, and any adverse sensor site problems. Acceptability will be determined through participant evaluation (Appendix C).

2.) We will calculate means and standard deviations of within-group and between-group differences from baseline to program completion (8th week) and post-program (12th week) on the outcomes of FOH, self-management, glycemic control (A1C), and GV.

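### No planned source for symptomatic or assistance-requiring hypoglycemia by arm: it is asked about only as prior history at Week 0, and sensor-site problems are the only adverse item tracked

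*Combined protocol and SAP*

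**What the plan says.** The Abstract describes hypoglycemia as a condition "which is life-threatening and has serious physical symptoms and psychological sequelae".

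What is planned on hypoglycemia:

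- **Self-report (3.2f1 and Table 1).** The instruments cover "previous history of hypoglycemia, fear of hypoglycemia, self-management behaviors" and related variables. The hypoglycemia instrument is the "Hypoglycemia Patient Questionnaire". Its row is labelled as previous hypoglycemia and its frequency is Week 0. The fear, self-management, self-efficacy, anxiety and mood, and distress scales are scheduled at Weeks 0, 8 and 12.
- **CGM (3.2f3).** "Subcutaneous interstitial glucose levels will be monitored during the run-in phase (over a period of 7 days) and the 8-week intervention", in both arms. "The amount of time spent in hypo- and hyperglycemia will be calculated", as percent and minutes below 70 and above 180 mg/dl.
- **Diary (3.2f2).** "A daily diary will be used to measure daily fear levels and perceptions of GV for FREE participants only".
- **Adverse items (3.2g, item 1).** Sensor failures and placement sites are logged, with "time to failure, and any adverse sensor site problems", as part of feasibility.
- **Outcome summaries (3.2g, item 2).** Within- and between-group means and SDs at weeks 8 and 12 are planned for fear, self-management, A1C and glycemic variability. Neither time below 70 mg/dl nor hypoglycemic episodes are named.

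The exposure tasks in 3.2e1 belong to the FREE arm. The examples include spending time alone, less snacking and "allowing glucose readings to reach lower safe levels". The control arm (3.2e2) has CGM wear and weekly sensor changes.

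**The concern.** The foreseeable harm that could differ between arms is a hypoglycemic episode with clinical consequences, because only one arm practises behaviors that may bring glucose down. The purpose of the pilot is to inform a larger trial. Followed as written, it could report lower fear and lower A1C in FREE with no count by arm of episodes that were symptomatic or needed another person's help, while sensor-site problems are counted carefully. Episodes not asked about at the time are hard to recover later.

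**Working it through.** The plan gives no figure to reproduce: the sample size of 10 is justified by feasibility alone, with no power statement and no event rate. The check sets each possible source against what an arm-level report of clinical hypoglycemia needs.

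| Source | Both arms? | After baseline? | Shows symptoms or need for help? |
|---|---|---|---|
| Hypoglycemia questionnaire (Table 1) | Yes | No, Week 0 only | Items not shown |
| CGM time below 70 mg/dl (3.2f3) | Yes | Yes, through week 8 | No |
| Daily diary (3.2f2) | No, FREE only | Yes | No; fear level and perceived variability |
| Sensor-site problems (3.2g) | Not limited to one arm | Yes | No |

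No row meets all three requirements.

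**Weeks 9 to 12.** Count weeks 1 to 12 as the time after the run-in. The 3.2f3 text ends CGM with the 8-week intervention, which leaves 4/12 = 33% of follow-up, or 10 × 4 = 40 of 10 × 12 = 120 planned person-weeks (20 of 60 per arm), with no described hypoglycemia measure. Specific Aim 2 and 3.2g item 2 nevertheless require glycemic variability at week 12, and Table 1 derives that from CGM. The frequency cells for the glycemic rows are run together in the supplied text and do not settle the matter.

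**Could an event occur in so small a trial?** FREE contributes 5 × 12/52 = 1.15 person-years. The documents give no rate of severe episodes, so the rates here are assumptions. With a Poisson count, P(at least one) = 1 − exp(−rate × 1.154):

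| Assumed rate per person-year | Expected events in FREE | P(at least one) |
|---|---|---|
| 0.2 | 0.23 | 21% |
| 0.5 | 0.58 | 44% |
| 1.0 | 1.15 | 68% |

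The range is wide. It shows only that an event is plausible enough to need a place to be recorded.

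**What could a count support?** With 0 of 5 affected, the exact one-sided 95% upper bound is 1 − 0.05^(1/5) = 45%, and the two-sided bound is 1 − 0.025^(1/5) = 52%. A count by arm is a description, not a comparison.

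**The case against.** The case for leaving the plan alone has several parts.

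1. **Hypoglycemia is measured.** Time below 70 mg/dl is calculated in both arms, and recordings are downloaded and examined weekly. This stands for biochemical hypoglycemia through week 8, and a reader who infers that the trial has no on-study hypoglycemia measure goes too far. What remains is that this metric cannot separate an asymptomatic dip from an episode needing help. The team's own preliminary study (3.1b) shows that the two kinds of data differ: 27% of participants reported and treated more presumed episodes than CGM recorded. That also warns that self-reported counts can run high, which is a reason to report both.

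2. **Weeks 9 to 12 may not be blank.** A reader might infer that an episode then would leave no trace. The documents do not support that, because two sections call for week-12 variability data. If CGM is worn around week 12, time below 70 mg/dl would be available for that period. The supportable statement is that the sections conflict.

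3. **The questionnaire is a baseline descriptor.** It sits under the heading for program outcomes, and one might infer that an intended outcome was mis-scheduled. Its row label says previous hypoglycemia, and the same block holds variables meant to characterize the sample. The objection stands, but it confirms that nothing else asks about clinical episodes after Week 0.

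4. **The file is incomplete.** Appendices A to D are cited but not supplied, and a separate safety document may exist. Weekly nurse contact in both arms would also let staff hear of events. So it would be wrong to say that the trial cannot report severe hypoglycemia; it has no planned source for doing so in the text available.

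5. **The exposure is bounded.** The protocol refers to safe levels, gives this as one example among several, and continues usual diabetes care. Nothing here implies that the program is unsafe.

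6. **Five per arm is too few.** True for any comparison, and the protocol calls itself a feasibility pilot. It is not a reason to leave events unrecorded.

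**Conclusion.** The point holds in this form: in the supplied text no planned source gives symptomatic or assistance-requiring hypoglycemia by arm after Week 0, although the exposure tasks are confined to FREE. Biochemical hypoglycemia is covered in both arms through week 8 but is missing from the 3.2g summary list. Coverage of the last third of follow-up is unclear because 3.2f3 conflicts with Specific Aim 2 and 3.2g.

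The change should be made, since it is cheap and the information is safety information, but no planned estimate depends on it. The conclusion assumes that no unsupplied appendix or safety document already provides for event recording. The event probabilities rest on assumed rates and carry no weight beyond plausibility.

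**What to change.** 1. **Table 1.** Add on-study clinical hypoglycemia in both arms at Weeks 8 and 12 and, if convenient, at the existing weekly nurse visits. Either repeat the questionnaire or add a short item covering the time since the last assessment. Because the questionnaire's items and recall period are not shown, state explicitly that episodes needing another person's assistance are included. Week 0 precedes the run-in, so ask for approximate dates to separate run-in episodes from those after randomization.
2. **3.2g.** Report by arm the number of participants with an episode and the number of episodes, with those needing assistance shown separately, alongside CGM time below 70 mg/dl and sensor-site problems. Label the table descriptive.
3. **Specific Aim 2, 3.2f3, Table 1 and 3.2g.** Reconcile whether CGM is recorded around week 12 and, if it is, over which days.
4. If another study document already covers event recording, cite it in 3.2g instead of steps 1 and 2.

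**Cost.** A few minutes per participant at visits already planned, and one extra table. Recall over 8 weeks is imprecise; asking at the weekly visits would reduce that through week 8. No clinical procedure changes.

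### Cleaning of the CGM data behind the glycemic variability outcomes is neither masked to arm nor tied to error rules fixed in advance

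*Combined protocol and SAP*

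**What the plan says.** Protocol section 3.2f3 describes two uses of the CGM recordings.

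- **Weekly review.** "At the end of each week, all data will be downloaded to the Dexcom Software and examined for glycemic trends and excursions". This covers both arms. What differs is who is given the result during the study: "The weekly glucose summary will be provided to subjects in the intervention group at each weekly session to provide feedback on their glucose trends". Controls receive theirs only after week 12. Section 3.2e3 adds, for FREE participants only, "weekly CGM downloads with GV analysis when they attend each session".
- **Outcome analysis.** "To analyze GV for study outcomes, the raw data will be downloaded to an EXCEL spreadsheet". Then: "The research staff will be trained on data cleaning, confirmation of regular calibration, identification of errors, and review of missing data or time-points". Five GV metrics follow (GlucSD, CONGA, CV%, IQR and MAGE), together with time below 70 and above 180 mg/dl.

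No section masks any role to arm. None defines an erroneous reading or asks for a record of what was removed. Section 3.2g lists means and SDs of within-group and between-group differences, and the second aim in section B says these will feed effect sizes for a larger trial.

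**The concern.** Participants and therapists cannot be masked to CBT, and apart from A1C the other outcomes under the second aim are self-reported. The CGM metrics are computed offline from stored files, so they can be protected from knowledge of arm at almost no cost. The plan does not use that opportunity.

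The readings most open to judgment are the extreme ones. A short run of very low values may be sensor error or true hypoglycemia, and someone has to decide. GlucSD, CV%, CONGA and MAGE all respond to that decision, and so does time below 70 mg/dl. If it is made with arm known and without a written rule, removal could differ slightly between arms. The resulting difference would look like an effect of FREE, or would hide one, in the figures used to plan the next trial.

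**Working it through.** The plan gives no figure on this point, so there is nothing to reproduce. Two checks show how far discretionary removal can move the metrics, and a third carries the result to arm level.

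**1. Trimming formula for GlucSD.** Inputs: SD = 52 mg/dl, the high-GV threshold in section 3.1b. Assumptions not in the documents: glucose is normally distributed, and there are 288 readings a day (one every 5 minutes). If a share *a* is removed from each tail, the SD is multiplied by sqrt(1 − 2zφ(z)/(1 − 2a)), where z is the upper *a* point of the standard normal and φ its density. For a = 0.01, z = 2.326 and φ(z) = 0.02665, so the ratio is sqrt(1 − 0.1240/0.98) = 0.935.

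| Removed per tail | Readings a day | SD ratio | GlucSD (mg/dl) | Change |
|---|---|---|---|---|
| 0.5% | 288 × 0.01 = 2.9 | 0.962 | 50.0 | −3.8% |
| 1% | 288 × 0.02 = 5.8 | 0.935 | 48.6 | −6.5% |
| 2% | 288 × 0.04 = 11.5 | 0.890 | 46.3 | −11.0% |

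**2. All five metrics, by simulation.** Real traces are autocorrelated, so 600 synthetic days per scenario were generated with three meal peaks plus autocorrelated noise (mean daily SD about 46 mg/dl). The glucose model, the 1-hour CONGA lag and the MAGE rule (excursions above 1 SD) are assumptions. Median change per day at 5-minute sampling:

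| Readings removed | GlucSD | CV% | MAGE | CONGA | IQR |
|---|---|---|---|---|---|
| 3 furthest from the median | −2.6% | −2.3% | −2.2% | −1.7% | −1.3% |
| 12 furthest from the median | −9.1% | −7.9% | −10.3% | −5.0% | −5.7% |
| A 3-reading run at 40 mg/dl (removed versus kept) | −2.7% | −3.5% | −8.2% | −7.6% | −0.8% |

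With few removals IQR moves least; with 12 it moves about as much as CONGA. At 15-minute sampling, 3 removals had larger effects: GlucSD −7.2%, CV% −6.1% to −9.4%, MAGE −6.1% to −11.6%, CONGA −3.7% to −17.5%, IQR −2.5% to −3.6%. These figures show direction and order of size only.

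**3. Arm level, 5 per arm.** Use the 1% row: 52.0 − 48.6 = 3.4 mg/dl per affected file.

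- One file of five: 3.4/5 = 0.7 mg/dl (1.3% of 52).
- Two files of five: 2 × 3.4/5 = 1.4 mg/dl (2.6%).
- All five in one arm and none in the other, as an upper bound: 3.4 mg/dl.

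With a between-person SD of 10 to 15 mg/dl (assumed), the standard error of a 5-versus-5 difference is SD × sqrt(2/5) = 6.3 to 9.5 mg/dl. In SD units, the one-file and two-file shifts run from 0.68/15 = 0.05 to 1.36/10 = 0.14. The upper bound is 3.4/15 = 0.23 to 3.4/10 = 0.34.

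For change from baseline, these shifts apply if the heavier removal falls on post-baseline days only. The same share removed at run-in would largely cancel.

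**The case against.** Two stronger readings are tempting, and the documents support neither.

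A reader might infer that the cleaners are the same people who run the weekly visits or give the FREE feedback. Section 3.2f3 assigns cleaning to research staff. Section 3.2e1 has FREE participants "have their RT-CGM site changed by a study staff member who is a registered nurse", and section 3.2e2 gives controls the same weekly visit. Sensor contact is therefore common to both arms, and whether the roles overlap is left open.

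A reader might also infer that FREE recordings get an extra look for excursions before analysis. Section 3.2f3 has the data of both arms downloaded and examined every week. Only the delivery of summaries during the study, and the GV analysis in section 3.2e3, are specific to FREE.

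Other points on that side are fair. Staff are to be trained, and the outcome data come from a separate raw download. The plan does not say that errors are found by eye or that extreme values are targeted. The protocol cites appendices that are not in the text reviewed, although none is cited as holding cleaning rules. The trial is a pilot of 10 with descriptive estimates and no test, and the plausible bias is small beside sampling error.

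These points limit the size and certainty of the problem but do not close the gap. Training does not mask anyone, a separate download does not hide arm, and sampling error is no reason to accept an avoidable bias in planning figures.

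**Conclusion.** The point holds in a narrow form. Error identification for the GV outcomes is left to staff who are not stated to be masked, under no written removal rule, and is not separated from the FREE-only GV analysis. Uneven removal could shift GlucSD, CV%, CONGA and MAGE, with IQR fairly resistant when few readings go.

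The likely size is modest: about 0.7 to 1.4 mg/dl in an arm's mean GlucSD if one or two of its five files lose 1% of readings per tail. This rests on the assumed glucose distribution and sampling interval, and on removal being uneven between arms, which the plan permits but nothing shows will happen. No error rate is at stake because no test of GV is planned. The change is low in priority, but worth making because it is so cheap.

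**What to change.** Add to section 3.2f3:

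1. Outcome cleaning is done in one pass, from the raw files of all 10 participants, under codes with arm removed and separately from the weekly FREE summaries.
2. One set of error rules is written before the pass and applied to every file. The team chooses the rules; they need only be fixed in advance and common to both arms.
3. The arm code is joined only after the GV metrics are computed.
4. The percent of readings removed is reported by arm.

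The cost is recoding 10 sets of files, with someone other than the cleaner holding the key. The final values may differ slightly from the weekly FREE summaries, and masking is imperfect if a cleaner recognizes a trace. Participant burden and clinical procedures do not change, and the larger trial would inherit a cleaning procedure already tried in practice.
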